#### **4.2.1.2 Vital signs**

Observed values and changes from baseline of pulse, systolic blood pressure, diastolic blood pressure, respiration rate, and body temperature, respectively, will be summarised by visit. The summary statistics presented will be minimum, 1st quartile, median, 3rd quartile, maximum, mean, and SD.

For each parameter with available criteria, the number and percentage of subjects with TELVC values will be summarised by year (using the same time windows as defined for AEs in Section 3.1.1 but Year 4 ending at Week 208 [LTE Visit 40/EDV] and not presenting the category ‘after Year 4’). Additionally, the number and percentage of subjects with at least 1 TELVC value will be presented. Percentages will be based on subjects with a measurement at baseline and at least 1 subsequent measurement of the variable (in the respective period).

For each parameter, the number and percentage of subjects with values below, within, or above the corresponding normal range will be presented as shift tables from baseline to maximum and minimum post-baseline value, respectively.

#### **4.2.1.3 Physical examination**

Observed values and changes from baseline of body weight will be summarised by visit. The summary statistics presented will be minimum, 1st quartile, median, 3rd quartile, maximum, mean, and SD.

#### **4.2.1.4 ECGs**

The number and percentage of subjects with normal; abnormal, not clinically significant; and abnormal, clinically significant ECG results will be presented as a shift table from baseline to last on-treatment value.

Observed values and changes from baseline of ECG values will be summarised by parameter and visit using descriptive statistics. The summary statistics presented will be minimum, 1st quartile, median, 3rd quartile, maximum, mean, and SD.

For each ECG parameter with available criteria, the number and percentage of subjects with Potentially Clinically Significant post-baseline values and Potentially Clinically Significant changes from baseline, respectively, will be presented by parameter and criterion.

#### **4.2.1.5 Flares based on Modified SELENA Flare Index**

The flare rate per subject year will be presented for mild/moderate flares, severe flares, and any flares.

#### **4.2.1.6 Laboratory variables**

Observed values and changes from baseline of laboratory data for haematology, clinical chemistry, and fasting lipid profile will be summarised by visit. The summary statistics presented will be minimum, 1st quartile, median, 3rd quartile, maximum, mean, and SD.

Shift plots (scatter plots) presenting baseline values versus minimum post-baseline values (neutrophils, lymphocytes, monocytes, and haemoglobin only) and maximum post-baseline values (creatinine, creatinine kinase, blood urea nitrogen, alanine aminotransferase, aspartate aminotransferase, bilirubin), respectively, will be provided. A diagonal reference line indicating no change and horizontal and vertical reference lines indicating the limits of the reference ranges will also be displayed on the shift plots.

If any laboratory variables show any unusual features (high or low values or a general shift in the data points) at specific visits, then shift plots of these data may also be produced. This will be discussed and agreed upon during the BDR meeting.

[figure not shown]
For each laboratory parameter with available criteria, the number and percentage of subjects with TELVC values will be summarised by visit. Additionally, the number and percentage of subjects with at least 1 TELVC value will be presented. Percentages will be based on subjects with a measurement at baseline and at least 1 subsequent measurement of the variable (at the respective visit).

[figure not shown]
The number and percentage of subjects with laboratory values below, within, or above the corresponding reference ranges [REDACTED] will be presented as shift tables from baseline to maximum and minimum on-treatment value, respectively.

[figure not shown]
Urinalysis will be summarised as shift tables from baseline to the last on-treatment value for each parameter. Furthermore, the number and percentage of subjects with treatment-emergent changes will be summarised by parameter. Percentages for the summary of treatment-emergent changes will be based on subjects with a measurement at baseline and at least 1 subsequent measurement of the variable.

[figure not shown]
In order to identify potential Hy's Law cases, a shift table of maximum on-treatment total bilirubin against maximum on-treatment ALT, and maximum on-treatment AST expressed as multiples of ULN will be presented.

A Listing including all subjects who meet the biochemical criteria for Hy's Law (potential Hy's Law), will be produced, and the relevant laboratory parameters will be tabulated showing all visits for these subjects.

[figure not shown]

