## 1.2 Study design

This is a Phase 3, multicentre, multinational, randomised, double-blind, placebo-controlled extension study characterising the long-term safety and tolerability of an IV treatment regimen of anifrolumab (300 mg) versus placebo in subjects with moderately to severely active systemic lupus erythematosus (SLE) who completed a Phase 3 study (D3461C00004 or D3461C00005) through the 52-week double-blind treatment period.

Approximately 575 subjects from Studies D3461C00004 or D3461C00005 (also referred to as the feeder studies) who were previously treated with anifrolumab (150 or 300 mg) or placebo for 52 weeks while receiving standard of care (SOC) treatment and who are willing to continue treatment may participate in the long-term extension (LTE) study if all eligibility criteria are met. Subjects will receive either a fixed IV dose of 300 mg anifrolumab every 4 weeks (Q4W) for up to 39 doses (LTE Week 0 to LTE Week 152) or placebo. Investigational product (IP) will be administered as an IV infusion via an infusion pump over a minimum of 30 minutes, Q4W.

In order to ensure that subjects with active SLE who enter the LTE will have adequate treatment of their disease in this 3-year blinded, placebo-controlled extension study, Investigators will be allowed to change the background SOC treatment for SLE during the course of the study. This LTE protocol allows for adding a new oral immunosuppressant or changing background immunosuppressants, as well as for flexible oral corticosteroids (OCS) use, so that subjects may achieve adequate control of their disease on study. However, it is recommended that subjects receive the lowest possible corticosteroid dose.

In the LTE study, treatment assignment will follow an Interactive Voice/Web Response System (IXRS) algorithm as follows:

- Subjects previously treated with anifrolumab 300 mg IV will stay on blinded treatment
- Subjects previously treated with anifrolumab 150 mg will switch to blinded anifrolumab 300 mg
- Subjects previously randomised to placebo will be re-randomised 1:1 to blinded anifrolumab 300 mg or placebo

Therefore, in the LTE study subjects will receive double-blind treatment with either anifrolumab 300 mg or placebo in an approximate ratio of 4:1.

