### **1.3 Number of subjects**

No formal comparisons are planned in this study; point estimates and confidence intervals (CIs) will be presented for each treatment group separately. The sample size is not based on statistical considerations, but is defined as all subjects who completed the treatment period in

the Phase 3 feeder Studies D3461C00004 or D3461C00005 (through Week 52) and met all study eligibility criteria. Assuming annual dropout rates of 30%, 30%, and 20% following placebo, anifrolumab 150 mg, and anifrolumab 300 mg, and that 90% of the subjects completing studies D3461C00004 or D3461C00005 enter the LTE, follow-up times of approximately 893, 517, and 1343 subject years for the “Randomised Anifrolumab 300 mg,” “Randomised Placebo,” and “All Anifrolumab” treatment groups are expected. Given this exposure, the 95% CIs for an AESI for which the observed incidence rate is 10 events in 1000 subject years will be 5.21 to 19.21 for “Randomised Anifrolumab 300 mg,” and 4.24 to 23.57 for “Randomised Placebo.” For an AESI for which the observed incidence rate is 1 event in 1000 subject years, the 95% CI will be 0.18 to 5.42 for “All Anifrolumab” (0.13 to 7.95 for “Randomised Anifrolumab 300 mg”), and 0.07 to 15.25 for “Randomised Placebo,” using the Rothman-Greenland Method ([Rothman and Greenland, 1998](#)).

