#### 2.1.6 Treatment groups for analysis

Summaries will be presented according to the following combined treatment groups. If not mentioned otherwise, data from subjects discontinuing from the investigational product in studies D3461C00004 or D3461C00005, or who elect not to participate in the LTE, will be considered up to the adjusted analysis-defined visit window of Week 52 (ie, up to Day 378).

Primary:

- **Randomised Anifrolumab 300 mg:** Subjects randomised to anifrolumab 300 mg in studies D3461C00004 or D3461C00005 using all data from start of feeder study to end of LTE.
- **Randomised Placebo:** Subjects randomised to placebo in studies D3461C00004 or D3461C00005 using data from start of feeder study up until switch to anifrolumab 300 mg or to end of LTE for subjects re-randomised to placebo in LTE, respectively.

Supportive:

- **Placebo Feeder + Placebo LTE:** Subjects randomised to placebo in Studies D3461C00004 or D3461C00005 and re-randomised to placebo in LTE using all data from start of feeder study to end of LTE. Data from subjects not randomised into the LTE for any reason but that would have been re-randomised to placebo are included in this treatment group up to Week 52. Subjects who are not randomised into the LTE study will be assigned to Placebo or anifrolumab 300 mg via a

separate randomization process in order to determine who would have been re-randomised to placebo.

- **All Anifrolumab:** Subjects randomised to anifrolumab in studies D3461C00004 or D3461C00005, regardless of dose, and subjects randomised to placebo in studies D3461C00004 or D3461C00005 and then re-randomised to anifrolumab 300 mg in LTE, using all data from start of feeder study or switch to anifrolumab, respectively, to end of LTE. Baseline data from the feeder study will be included for all subjects.

Additional supportive:

- **Placebo Feeder + Anifrolumab 300 mg LTE:** Subjects randomised to placebo in studies D3461C00004 or D3461C00005 and then re-randomised to anifrolumab 300 mg in LTE using data from start of feeder study to end of LTE. Data from subjects not randomised into the LTE for any reason, but that would have been re-randomised to anifrolumab 300 mg are included in this treatment group up to Week 52. Subjects who are not randomised into the LTE study will be assigned to Placebo or anifrolumab 300 mg via a separate randomization process in order to determine who would have been re-randomised to anifrolumab 300 mg.

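### Cumulative laboratory and ECG percentages are not adjusted for follow-up: with no drug effect, anifrolumab could show up to about 1.7 times as many subjects with an uncommon abnormality as Randomised Placebo

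*SAP*

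**What the plan says.** **Groups compared.** SAP 4.2.1 summarises safety variables by combined treatment group unless stated otherwise, and names Randomised Anifrolumab 300 mg against Randomised Placebo as the main comparison. Under SAP 2.1.6 the anifrolumab group keeps its data to the end of the LTE. Randomised Placebo is built "using data from start of feeder study up until switch to anifrolumab 300 mg or to end of LTE for subjects re-randomised to placebo". SAP 1.2 fixes the split: "Subjects previously randomised to placebo will be re-randomised 1:1 to blinded anifrolumab 300 mg or placebo".

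**Outputs affected.**
- Laboratory (SAP 4.2.1.6): "Additionally, the number and percentage of subjects with at least 1 TELVC value will be presented". Values against the reference ranges are shown as "shift tables from baseline to maximum and minimum on-treatment value, respectively". The section also plans scatter plots of baseline against worst post-baseline value, counts of treatment-emergent urinalysis changes, and a Hy's Law table of maximum on-treatment values.
- ECG (SAP 4.2.1.4): the number and percentage of subjects with potentially clinically significant values "will be presented by parameter and criterion".

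None of these has a time denominator or a split by period.

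**Outputs not affected in this way.** The ECG category shift and the urinalysis shift use the last on-treatment value. Laboratory TELVC is also summarised by visit.

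**Treatment elsewhere in the SAP.** AE rates use exposure or time at risk (SAP 3.1.1), flares are per subject-year (SAP 3.1.5), and vital-sign TELVC is split by year (SAP 4.2.1.2).

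**The concern.** The chance that a subject ever crosses a threshold, and the size of the subject's worst value, both rise with time observed and number of samples. Placebo subjects who switch contribute to Randomised Placebo none of the ten scheduled post-entry LTE laboratory draws (Weeks 4, 8, 12, 24, 36, 52, 76, 104, 128 and 156) and none of the LTE ECGs at Weeks 52, 104 and 156 (Protocol Tables 2 and 3). Their counterparts on anifrolumab 300 mg contribute all of them while they remain.

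A plain percentage of subjects therefore favours the group observed for less time. At stake is the cumulative part of the haematology, chemistry, urinalysis and ECG safety comparison. An excess on anifrolumab in these tables could come from longer observation rather than from the drug.

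**Working it through.** **Inputs (SAP 1.3 and 1.2).** "Assuming annual dropout rates of 30%, 30%, and 20% following placebo, anifrolumab 150 mg, and anifrolumab 300 mg"; "90% of the subjects completing studies D3461C00004 or D3461C00005 enter the LTE"; 1:1 re-randomisation of feeder placebo subjects; one feeder year plus three LTE years. The plan's own result is "follow-up times of approximately 893, 517, and 1343 subject years for the" Randomised Anifrolumab 300 mg, Randomised Placebo and All Anifrolumab groups.

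**1. Reproduce the plan's subject-years.** Spread dropout d evenly within each year, so that a subject starting a year contributes 1 − d/2.
- Anifrolumab 300 mg: 0.90 + 0.80 × 0.90 × 0.90 × (1 + 0.80 + 0.64) = 2.481 years per subject.
- Randomised Placebo: 0.85 + 0.70 × 0.90 × 0.5 × 0.85 × (1 + 0.70 + 0.49) = 1.436 years per subject.
- 893/2.481 and 517/1.436 both give about 360 subjects. With 360 each, the totals are 893.2 and 517.1.

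The follow-up ratio is 2.481/1.436 = 1.73. Exponential dropout gives 2.471 and 1.421 years, ratio 1.74.

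**2. 'Ever abnormal' with no drug effect.** Take the same constant hazard h = −ln(1 − annual risk) in both groups, with dropout hazard λ = −ln(1 − d). Then

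P(ever) = h/(h+λ) × [1 − e^−(h+λ)] + c × e^−(h+λ) × h/(h+λ) × [1 − e^−3(h+λ)],

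where c = 0.9 for anifrolumab and 0.45 for Randomised Placebo. At 10% annual risk:
- Anifrolumab: 0.3207 × 0.28 + 0.9 × 0.72 × 0.3207 × 0.6268 = 0.220.
- Placebo: 0.2280 × 0.37 + 0.45 × 0.63 × 0.2280 × 0.7500 = 0.133.

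| Annual risk | Anifrolumab | Randomised Placebo | Ratio | Difference (points) |
|---|---|---|---|---|
| 1% | 2.4% | 1.4% | 1.73 | 1.0 |
| 5% | 11.7% | 6.9% | 1.70 | 4.8 |
| 10% | 22.0% | 13.3% | 1.66 | 8.7 |
| 30% | 52.6% | 35.2% | 1.49 | 17.4 |
| 50% | 70.9% | 52.9% | 1.34 | 18.0 |
| 90% | 90.4% | 83.3% | 1.09 | 7.2 |

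**3. Remove the dropout difference.** With equal dropout of 10%, 20% or 30% in both groups, the step 1 formula gives follow-up ratios of 1.52, 1.47 and 1.41. That part comes from the switch alone.

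**4. Count samples instead of time.** The LTE schedule is in the Protocol; the feeder schedule is not, so it is varied as an assumption. Expected laboratory samples per subject (feeder + LTE):

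| Assumed feeder draws | Anifrolumab | Randomised Placebo | Ratio |
|---|---|---|---|
| Every 4 weeks | 11.55 + 5.69 = 17.25 | 10.79 + 2.21 = 12.99 | 1.33 |
| Every 12 weeks | 3.51 + 5.69 = 9.20 | 3.25 + 2.21 = 5.46 | 1.69 |
| Weeks 24 and 52 | 1.70 + 5.69 = 7.40 | 1.55 + 2.21 = 3.76 | 1.97 |

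For ECGs the ratio is 1.32, 1.53 or 1.86 with four, two or one feeder recordings. Restricting the denominator to subjects with a post-baseline value lowers these slightly (laboratory, 1.33 to 1.31 and 1.69 to 1.63).

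**5. The supportive placebo column.** Placebo Feeder + Placebo LTE: 0.85 + 0.70 × 0.90 × 0.85 × 2.19 = 2.023 years, and 2.481/2.023 = 1.23. For common abnormalities the null ratio falls to 1.13 (50% annual risk) and 1.05 (90%).

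**6. Check the remedies.**
- By period, exponential dropout leaves 0.896/0.841 = 1.07 in Year 1 and 2.187/1.842 = 1.19 per LTE entrant.
- First occurrence over time at risk gives a null ratio of 1.0 under a constant hazard. If detection follows the number of samples, it gives about 1.33/1.74 = 0.76 to 1.97/1.74 = 1.13.
- Dividing first occurrences by total exposure over-corrects: 1.66/1.74 = 0.95, 1.49/1.74 = 0.86 and 1.34/1.74 = 0.77 at annual risks of 10%, 30% and 50%.

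**The case against.** The strongest reply is that these displays are descriptive and secondary, and that the SAP offers other views of the same data. No formal comparison is planned (SAP 1.3). The primary outcome, AESI and SAE rates, is exposure-adjusted. Laboratory deteriorations that are serious or lead to discontinuation are reported as AEs (Protocol 6.6.6) and so enter the AE rates. Combined tables also carry the Placebo Feeder + Placebo LTE column (SAP 4.1.3), laboratory TELVC is shown by visit, exposure is tabulated by group, and LTE-only summaries are promised in general terms (SAP 2.1.6). The Hy's Law table serves mainly to find cases, and it and the laboratory shifts are limited to on-treatment values.

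Most of this stands and limits the consequence. A reader might infer that the tables leave no way to tell a signal from longer observation; the documents do not support that. But SAP 4.2.1 makes Randomised Placebo the main comparator and labels the other placebo column supportive. Neither SAP 4.2.1.4 nor 4.2.1.6 asks for LTE-only versions of the cumulative outputs, and the by-visit TELVC rows do not cover the shifts, the urinalysis changes or the ECG counts. Descriptive safety tables are still read by comparing columns.

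**Conclusion.** The point holds as a bias in how the cumulative outputs are specified, and it should be corrected. Under the plan's assumptions the null ratio of 'ever abnormal' subjects is up to about 1.7 for uncommon abnormalities (annual risk up to about 10%). It falls to 1.49 at 30% and 1.09 at 90%, although the absolute gap peaks near 18 points. Every scenario examined puts the excess on anifrolumab.

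Two stronger readings are tempting and not supported. One is that 1.7 applies to every abnormality: it is essentially the follow-up ratio, and by sample count the figure is about 1.3 to 2.0. The other is that the sampling schedule alone produces it: part comes from the assumed 20% against 30% dropout, and the switch alone gives about 1.4 to 1.5.

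The result rests on constant hazards, the plan's dropout and entry figures, groups of about 360 (back-calculated, not stated), and assumed feeder schedules. The Hy's Law table is affected to a lesser extent, because it is mainly case-finding. The primary AESI and SAE rates are not affected.

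**What to change.** In SAP 4.2.1.4 and 4.2.1.6, present the cumulative outputs by period, with subjects assessed in that period as the denominator. Either of two splits would do:
- by year, as SAP 4.2.1.2 does for vital-sign TELVC; or
- feeder Year 1 by feeder randomised group, and LTE only by LTE treatment group.

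This should be the main remedy, because it compares subjects on the same part of the schedule.

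For combined-group 'at least 1' counts, add first-occurrence rates per 100 subject-years at risk, using the alternative event rate in SAP 3.1.1 rather than the rate over total exposure. State beside them that they correct for time but not for different sampling density in the feeder and LTE periods.

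The cost is SAP wording, period filters on existing table programs, and more tables; no new data are needed. A small dropout imbalance remains, about 1.07 in Year 1 and 1.19 in the LTE under the plan's assumptions, so the periods should not be described as equally sampled.

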### **4.2.3 Presentation of study population**

#### **4.2.3.1 Subject disposition**

Beside the summary of protocol deviations, all summaries of subject disposition will be presented by combined treatment group as well as by LTE treatment group for the full analysis sets.

The number and percentage of subjects with the following study outcomes will be summarised. In the presentation by LTE treatment group, the first 5 categories will not be presented.

- Completed the Phase 3 feeder studies up to and including Week 52 (Visit 14/EDV) and either enrolled to LTE, or completed 12 weeks of follow-up after their last dose of IP (Follow-up Visit 2, or Week 52 for subjects who prematurely discontinued IP > 12 weeks prior)
- Withdrew from the Phase 3 feeder studies including reason for withdrawal
- Completed treatment with investigational product in the Phase 3 feeder studies up to and including Week 48 (i.e., with last administration of investigational product at Visit 13)
- Permanently discontinued the treatment with investigational product in the Phase 3 feeder studies including reason for withdrawal
- Randomised to the LTE study
- Completed the LTE study up to and including Week 208 (LTE Visit 40/EDV)
- Withdrew from the LTE study including reason for withdrawal
- Completed treatment with investigational product in the LTE study up to and including Week 204 (LTE Week 152, ie, with last administration of investigational product at LTE Visit 39)
- Permanently discontinued the treatment with investigational product in the LTE study including reason for withdrawal

This summary will be repeated for the first 5 categories by feeder study (D3461C00004 and D3461C00005) and corresponding feeder study treatment group. The number and percentage of subjects randomised to the respective study as well as the randomised treatment in the LTE study will also be included in the summary by feeder study.

Furthermore, the number and percentage of subjects remaining on investigational product, discontinued investigational product but remain on study, and withdrawn from study will be summarised by 6-month intervals (i.e., at weeks 24, 52 [both for combined data from feeder and LTE study only], 76, 104, 128, 156, 180, and 204). This summary will be presented for all given time points even with less than 25 subjects.

A summary of number and percentage of subjects in each population will be provided.

Important protocol deviations, COVID-19 related important protocol deviations, and important protocol deviations not related to COVID-19 occurring during the LTE study will be summarised by LTE treatment group.

The number and percentage of subjects with the following study outcomes will be summarised for the LTE study by LTE treatment group.

- Subjects randomised prior to the start of the COVID-19 pandemic
  - Subjects no longer in the study at the start of the COVID-19 pandemic
  - Subjects ongoing in the study at the start of the COVID-19 pandemic
- Subjects with at least one disruption due to the COVID-19 pandemic
  - Subjects with visit impaired
  - Subjects with study drug impacted
  - Subject who discontinued treatment due to COVID-19
  - Subjects who withdrew from study due to COVID-19.

Start date of the COVID-19 pandemic is 11-Mar-2020 as declared by the World Health Organization.

#### **4.2.3.2 Demographic and baseline characteristics**

All summaries of demographic and baseline characteristics will be presented for the full analysis set.

Summaries of demographic data, past and current medical history (including cardiovascular risk factor summary) and prior medication use will be based on information as recorded in the phase 3 feeder study for all subjects, regardless of whether the data from the phase 3 feeder studies will be included in post-baseline summaries for this treatment group. E.g. for the All Anifrolumab treatment group, demographics, medical history and prior medications from the phase 3 feeder study will be presented for the subjects randomised to placebo in the phase 3 feeder studies.

Demography and baseline characteristics will be presented by descriptive statistics and by combined treatment group, by LTE treatment group, and overall (i.e., including a total column).

Past and current medical history will be summarised separately by combined treatment group, MedDRA system organ class, and preferred term. Furthermore, the number and percentage of subjects with the cardiovascular risk factors will be presented by risk factor.

Prior and concomitant medications will be summarised separately by combined treatment group, WHO-DD Anatomical Main Group (ATC level 1), and preferred term.

Disease related treatments will be summarized by combined treatment group and by LTE treatment group. The number and percentage of subjects with at least 1 treatment in the categories given in Section 3.3.3 will be presented at baseline and every 3 months starting with Week 52 (high-level categories as given in Section 3.3.3) together with the

corresponding change from baseline (added, no change, discontinued). Percentages will be based on the number of subjects with at least one assessment at the corresponding visit.

